6.6 Values Below LLQ

Concentrations for TTP488 below the lower limit of quantification (LLQ) for the assay will be set to zero for the purpose of analysis.

7 Analysis Deviations

All statistical analyses and summary information will be generated according to this analysis plan. Any deviation from this plan will be documented in the clinical study report. Exploratory analyses are permitted per protocol; those analyses will not be considered to be deviations.

8 Software

All analyses will be done using SAS Version 9.4 or later.

9 Data Displays

The plans for displaying data will be appropriate for open-label extension studies.

Planned displays will include, but are not limited to, the following:

- Summary of Accountability (number enrolled, completing, withdrawn, by reason; listing of withdrawals with study day and reason)
- Summary of Demography and Background Data
- Summary of Adverse Events
- Summary of Adverse Events by severity and by relatedness
- Summary of Vital Signs (change over time; criteria of potential clinical concern)
- Summary of Laboratory Data, including LFTs (change over time, TEAV, and criteria of potential clinical concern)
- Summary of PK Data
- Summary of PD Data
- Summary of Efficacy Data (ADAS-cog, CDR-sb, CDR-global, MMSE, ADCS-ADL, NPI)
- Listing of Demography
- Listing of Dosing
- Listing of all Adverse Events
- Listing of all Adverse Events that resulted in Death
- Listing of all Serious Adverse Events
- Listing of all Adverse Events resulting in Study Termination
- Listing of Treatment-emergent Abnormal Values of Potential Clinical Concern for Clinical Laboratory Data
- Listing of Vital Signs Data
- Listing of QTc data that meet criteria of potential concern as described in ICH E14
- Listing of azeliragon, TTP1494, TTP2266, TTP2123 Concentration Data
- Listing of plasma A β (total, 1-40 and 1-42)

In addition to the data summaries and listings described above, the set of displays will include clinical laboratory normal ranges (with units) and also a display of the MedDRA mapping glossary, which will display the verbatim text as reported by the investigator, the LLT, PT, and SOC.

10 Values of Potential Clinical Concern

Parameter	Threshold (study-specific threshold calculated)
Hematology	
Hemoglobin	<8.5 g/dL
Hematocrit	<25 %
WBC (Leukocytes)	<0.6 x LLN (<2.1 10 ³ /uL)
Platelets	<0.5 x LLN (<70 10 ³ /uL)
Total Neutrophils (Abs)	<0.8 x LLN (<0.8 10 ³ /uL)
Lymphocytes (Abs)	<0.6 x LLN (<0.6 10 ³ /uL)
Chemistry	
Total bilirubin	>2.5 x ULN (>2.7 mg/dL)
AST	>3 x ULN (>102 U/L)
ALT	>3 x ULN (>123 U/L)
Alk Phosphatase	>3 x ULN (>348 U/L)
Creatinine	>2 mg/dL
BUN	>1.4 x ULN (30.8 mg/dL)
Glucose	≤70 mg/dL or ≥270 mg/dL
Uric acid	>12 mg/dL
Sodium	<125 mmol/L or >155mmol/L
Potassium	<3.0 mmol/L or >6.0 mmol/L
Bicarbonate	<16 mmol/L
Calcium	<6.0 mg/dL and >13.0 mg/dL
Triglycerides	>750 mg/dL
Electrocardiogram	
Heart Rate	<50 bpm and ≥/=25% decrease from baseline >100 bpm and ≥/=25% increase from baseline
PR interval	≥200 msec and ≥25% increase from baseline
QRS interval	≥200 msec and ≥25% increase from baseline
QTc interval	≥500 msec ≥30-60 msec increase >60 msec increase
Vitals (sitting)	
SBP	≥190 mmHg (entry is <180 mmHg) Systolic <80 mm Hg Decrease from baseline ≥30 mmHg
DBP	≥120 mmHg (entry is <105) <50 mm Hg

Parameters not provided with specific thresholds for clinical concern: RBC count, eosinophils, basophils, monocytes, direct or indirect bilirubin (just total as shown above), chloride, albumin, total protein, insulin, total cholesterol, HDL, LDL, urinalysis, pulse rate from VS (rely on ECG heart rate).

11 References

- Berg, L. Clinical Dementia rating (CDR). *Psychopharmacol Bull.* 1988;24:637-9.
- Little, RJA, and Rubin, DB. (1987). *Statistical analysis with missing data.* New York: John Wiley and Sons.
- Rubin, D.B. (1976, December). Inference and Missing data. *Biometrika*, Volume 63, Issue 3 (Dec., 1976), 581-592.
- ICH. (1996, July 30). ICH Harmonized tripartite guideline: Structure and content of clinical study reports (E3). International Conference on Harmonization of Technical Requirements for Registration of Pharmaceuticals for Human Use.
- ICH. (1997, July 17). ICH Harmonized tripartite guideline: General considerations for clinical trials (E8). International Conference on Harmonization of Technical Requirements for Registration of Pharmaceuticals for Human Use.
- ICH. (1998, February 5). ICH Harmonized tripartite guideline: Statistical principles for clinical trials (E9). International Conference on Harmonization of Technical Requirements for Registration of Pharmaceuticals for Human Use.

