4.2.4 Clinical laboratory assessments

Routine clinical laboratory data will be summarized with descriptive statistics on assessment values and change from Baseline. Routine clinical laboratory data will also be evaluated on the basis of laboratory-defined reference ranges and clinically important values or changes, as defined in this document (Section 10). Routinely collected laboratory safety data that are not required by the protocol will be considered source data, and will not be captured for inclusion into the study database. In TTP488-303, the clinical laboratory blood samples will be collected at Months 6, 12, 18 and 24 or in the event of early termination.

Definition:

- A treatment-emergent abnormal value (TEAV) is a laboratory value that is abnormal after administration of study medication that was normal prior to study medication administration.
- A TEAV of potential clinical concern is a value or change that meets criteria specified in this SAP in Section 10.

Laboratory analytes in this study include:

- Hematology
 - Hemoglobin
 - Hematocrit
 - Erythrocyte (RBC) count
 - Platelet count
 - Total leukocyte (WBC) count
 - MCV
 - Leukocyte differential (percent and total)
 - Total neutrophils
 - Eosinophils
 - Monocytes
 - Basophils
 - Lymphocytes
- Clinical chemistry
 - BUN
 - Creatinine
 - Glucose
 - HbA1c
 - Calcium
 - Sodium
 - Potassium
 - Chloride
 - Bicarbonate
 - AST
 - ALT
 - GGT
 - LDH
 - Total bilirubin
 - Alkaline phosphatase
 - Uric acid
 - Albumin
 - Total protein

Safety variables of analysis include:

- Subjects with TEAVs
- Subjects with TEAVs of potential clinical concern (based on criteria in this SAP)
- Subjects with a TEAV in a liver function test (LFT)

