5.3.3 Routine Clinical Laboratory Measurements

Because “exacerbations” of pre-existing abnormalities in laboratory analytes are examined using clinical judgment and are reported as TEAEs, additional analysis on TEAVs is limited to subjects with values that are normal prior to dosing and abnormal after dosing. Potentially clinically significant abnormalities in laboratory analytes are to be reported as TEAEs and summarized as clinical TEAEs.

Subjects with clinical laboratory data meeting the criteria in Section 10 of this SAP for values of potential clinical concern will be flagged and summarized. Proportions of subjects with clinical laboratory values of potential clinical concern will be examined for the treatment groups.

For each post-Baseline assessment, descriptive statistics are provided for the assessment value and the change from Baseline to the assessment with mean, median, standard deviation, minimum, and maximum at each assessment time.

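### The calcium criterion in SAP Section 10 joins its low and high limits with *and*, so no single value can meet it and the flag would be empty if programmed as written

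*SAP*

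**What the plan says.** The table in SAP Section 10 (Values of Potential Clinical Concern) gives the calcium criterion as "<6.0 mg/dL and >13.0 mg/dL".

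The other chemistry rows with both a low and a high limit are worded differently:

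- glucose: "≤70 mg/dL or ≥270 mg/dL"
- sodium: "<125 mmol/L or >155mmol/L"
- potassium: "<3.0 mmol/L or >6.0 mmol/L"

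The word *and* also appears in the ECG rows. There it joins an absolute limit to a percentage change from baseline. The PR and QRS rows both read "≥200 msec and ≥25% increase from baseline", and the heart rate row pairs its limits with a 25% change in the same way.

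Two sections put the table to use. SAP 4.2.4 gives the definition: "A TEAV of potential clinical concern is a value or change that meets criteria specified in this SAP in Section 10". SAP 5.3.3 gives the output: "Subjects with clinical laboratory data meeting the criteria in Section 10 of this SAP for values of potential clinical concern will be flagged and summarized". SAP 5.3.3 adds that the proportions will be examined for the treatment groups, and SAP Section 9 plans a laboratory summary and a listing based on the same criteria. SAP Section 7 commits the analyses to the plan and requires deviations to be documented in the clinical study report.

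**The concern.** The calcium row describes two regions that do not overlap and asks for a value in both. A program that follows the row literally can never flag a calcium result, however extreme. The output would then show no subjects in each group, and from that row alone a reader could not tell a true absence of extreme values from a rule that cannot fire.

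This is operative text: the row feeds a planned flag, summary and listing. The programmer is left to choose between following the SAP and getting an empty row, or coding the evident intent and departing from the written rule. A prespecified threshold should not leave that choice open.

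**Working it through.** The plan states no figure for this point, so there is none to reproduce. No sample size, power or alpha is involved, and the check is one of logic.

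**Inputs.** The calcium limits, 6.0 and 13.0 mg/dL, and their connector come from SAP Section 10. The unit to which the criterion applies, a single value or change, comes from SAP 4.2.4.

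**Step 1: can the criterion be met as written?** It requires x < 6.0 and x > 13.0 for the same x. Since 6.0 < 13.0, the set {x < 6.0} ∩ {x > 13.0} is empty. The two regions are 13.0 − 6.0 = 7.0 mg/dL apart.

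**Step 2: confirmation on a grid.** Calcium was taken from 0 to 30 mg/dL in steps of 0.1, which gives 301 values.

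| Connector | Below 6.0 | Above 13.0 | Values meeting the criterion |
|---|---|---|---|
| *and* (as written) | – | – | 0 of 301 |
| *or* | 60 | 170 | 60 + 170 = 230 of 301 |

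The other 71 values lie from 6.0 to 13.0 inclusive. The grid shows only that the criterion can be met with *or*. The count of 230 depends on the range chosen and says nothing about how many subjects would be flagged.

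**Step 3: are other rows affected?** The sodium and potassium rows, with *or*, can be met (50 of 81 integer values from 100 to 180 mmol/L, and 90 of 121 values from 0 to 12 mmol/L in steps of 0.1). The heart rate row, with *and*, can also be met. At an assumed baseline of 80 bpm and integer rates from 30 to 159, 20 values satisfy the low criterion and 59 the high one. Of the rows tested, only calcium cannot be met.

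**Step 4: does other text rescue the row?** One could read it at subject level, with one value below 6.0 and a different value above 13.0. SAP 4.2.4 speaks of a value or change, which does not support that reading, and it would still miss a subject with only low or only high values. No other section gives a different calcium rule. Section 10 closes with a list of parameters that have no specific threshold, and calcium is not on it, so a working threshold was intended.

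**Step 5: what else in the plan would show an extreme calcium value?**

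- SAP 4.2.4 lists calcium among the analytes and counts values that were normal before dosing and abnormal afterwards. This does not cover a subject whose calcium was already abnormal at baseline.
- SAP 5.3.3 gives descriptive statistics, including minimum and maximum, at each post-baseline assessment.
- SAP 6.5 brings unscheduled values into summaries over time, such as the minimum and maximum.
- SAP 5.3.3 has potentially clinically significant laboratory abnormalities, and exacerbations of existing ones, reported as adverse events.
- SAP 4.2 has medically qualified staff review listings of the laboratory data.

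**The case against.** The best reply is that nobody would be misled. Three neighbouring rows use *or*, the intended meaning is obvious, and a competent programmer would query an impossible condition or code the sensible one. The table is also loosely drafted: in the text available, the heart rate, QTc and blood pressure cells list alternatives with no connector at all, so a reader must already supply *or* there. No section defines what the connectors mean, so it would be too much to say that *and* carries a formal programming definition in this table.

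That reply stands as far as it goes. A reader might infer that the calcium flag is certain to be zero. The documents support only the conditional statement that it is zero if the row is coded literally.

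A reader might also infer that calcium abnormalities would disappear from the safety report, or that an empty row would pass as evidence that there were none. The documents do not support this either, because the other routes in step 5 of the working remain. A scheduled calcium result below 6.0 or above 13.0 mg/dL would appear in the by-visit minimum or maximum.

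Nor is Section 10 a decision rule for a primary outcome. Laboratory tests are among the primary endpoints in Protocol 2.2. However, the laboratory variables in Protocol 9.3 are treatment-emergent abnormal values, liver injury criteria and mean changes, and the Section 10 flag is an additional SAP variable. SAP Section 2 has no formal hypotheses, and SAP Section 5 makes safety evaluation descriptive.

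The reply does not make the row correct. That the intent can be guessed is a reason to correct the text, since under SAP Section 7 the outputs are meant to follow it.

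**Conclusion.** The calcium row is wrong as written: no single value can satisfy it. On the literal reading, the calcium entry in the potential-clinical-concern flag, summary and listing is empty whatever the data show.

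The size is modest. One analyte in one descriptive output is affected, and no inference or study decision depends on it. The number of subjects with calcium outside the limits is probably small, but the documents give no figure from which to estimate it.

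The conclusion rests on two assumptions: that the row is programmed as it stands, and that the criterion is applied to single values, as SAP 4.2.4 says. It takes no view on whether 6.0 and 13.0 mg/dL are suitable limits.

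**What to change.** In the calcium row of SAP Section 10, replace *and* with *or*, so that the row has the same form as the glucose, sodium and potassium rows. Leave both limits as they are.

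If the safety programs have already been written, check how the calcium row was coded. If *or* was coded before the SAP is corrected, record that in the clinical study report as SAP Section 7 requires.

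The cost is one word in the SAP and, at most, one line of code. Data collection and patient management are unaffected.

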4.2 EXCLUSION CRITERIA

Participants presenting with any of the following will be excluded from participation in the study.

1. The subject is felt by the investigator to be unsuitable (on the basis of health, compliance, caregiver availability, or for any other reason) for inclusion in the study.
2. Subjects with serious suicide risk. If there are “yes” answers on items 4, 5 or on any behavioral question of the C-SSRS, a suicide risk assessment must be done by a qualified mental health professional with expertise in the evaluation of suicidality in the elderly (e.g., psychiatrist, geriatrician or neurologist specializing in treatment of patients with AD) to determine whether it is safe for the subject to participate in the study.
3. Subjects demonstrating a QTcF > 480 msec or a >45 msec increase from the TTP488-301 Baseline value based on the locally read ECG performed at the TTP488-301 Month 18 Visit (TTP488-303 Baseline). Participants with known history of bundle branch block (either right or left) are allowed if absolute QTcF value does not exceed 500 msec. Participants with a functioning pacemaker, indicated by an ECG displaying paced rhythm, are allowed with no QTc upper limit.
4. Other acute or chronic medical or psychiatric condition or laboratory abnormality that may increase the risk associated with study participation or investigational product administration or may prevent the subject from completing the 2-year study or may interfere with the interpretation of study results and, in the judgment of the investigator, would make the subject inappropriate for entry into this trial.

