7.1.2 Electrocardiogram

12-lead ECG should be recorded after participants have been resting at least 5 minutes in the supine position. Each original recording will be evaluated by the PI or designee following the measurement. The interpretation of results will follow the categories “normal,” “abnormal, NCS,” or “abnormal, CS”. An abnormal measurement may be repeated at the PI or designee discretion. If the abnormal ECG measurements are considered as clinical significant, the abnormality will be recorded as AE in the eCRF.

When assessing eligibility at the Baseline visit, the presence of BBB (either left or right) is allowable as long as the absolute QTcF value does not exceed 500 ms and the subject does not have any other cardiac exclusions as described in exclusion criterion 4. When an ECG displays a paced rhythm indicating a functioning pacemaker is present, there is no upper limit as long as there are no related cardiac exclusions. Note. If there is no known history of BBB (either right or left), the discovery of such should prompt further investigation prior to proceeding with screening.

At the Baseline visit, the participant’s TTP488-301 Month 18 ECG will be reviewed locally in order to verify continued eligibility for the study. If the QTcF is >480 msec based on the local QTcF reading, the participant is not eligible. If the QTcF represents an increase from TTP488-301 Baseline of > 45 msec, the participant is not eligible.

At any time during the study, a subject with an absolute QT > 480 msec or an increase from baseline in QTcF > 45 msec should prompt a call to the Sponsor’s medical monitor for guidance on how to proceed.

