4.2 Safety Variables

Safety is monitored in this study by collection of adverse events, vital signs, electrocardiography, and clinical laboratory measures. It is noted that all untoward events or experiences are reported as adverse events regardless of whether they are identified by clinical observation, subject reporting, physical examination, clinical laboratory test result, electrocardiography, or any other examination or test. It is noted that listings are reviewed by medically qualified individuals of vital signs, laboratory data, electrocardiograms (ECG), and all safety data from all other sources to ensure that safety signals are identified and reported in the analysis of the safety data from this study.

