5.3.5 Electrocardiography

The heart rate, QT, PR, and QRS intervals will be recorded at each assessment time. No formal inferential statistics will be applied to the ECG data.

For each post-Baseline assessment, descriptive statistics are provided for the assessment value and the change from Baseline to the assessment with mean, median, standard deviation, minimum, and maximum at each assessment time.

In addition, the number of subjects with corrected and uncorrected QT values >500 msec will be summarized. Values from individual tracings within the triplicate measurement on Day 1, time 0 hour that are >500 msec will not be included in the categorical analysis unless the average from that triplicate measurement is also >500 msec.

Electrocardiography data will be summarized by Baseline and Change from Baseline to each scheduled assessment time with descriptive statistics.

Corrections to QT intervals will be made by Fridericia's method (QTcF). Categorical analysis will be done consistent with ICH E14, "Clinical evaluation of QT/QTc interval prolongation and proarrhythmic potential for non-antiarrhythmic drugs" (October 2005).

In accordance with ICH E14, subjects will be categorized and summarized as described above according to:

- Absolute QTc interval prolongation:
 - QTc interval > 450
 - QTc interval > 480
 - QTc interval > 500
- Change from Baseline in QTc interval:
 - QTc interval increases from Baseline > 30
 - QTc interval increases from Baseline > 60.

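### SAP Section 10 gives QRS the PR criterion unchanged, so its 25% limb has no effect below a 160 msec baseline and the plan's only categorical QRS rule is insensitive

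*SAP*

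**What the plan says.** The table in SAP Section 10 (Values of Potential Clinical Concern) has one row for PR and one for QRS. Both carry the same text: "≥200 msec and ≥25% increase from baseline". The heart rate row also joins an absolute limit to a 25% change with an *and*. The QTc row is built differently: it lists an absolute limit and two change limits as separate entries.

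SAP 5.3.5 states that "The heart rate, QT, PR, and QRS intervals will be recorded at each assessment time", and then that "For each post-Baseline assessment, descriptive statistics are provided for the assessment value and the change from Baseline to the assessment". The maximum is among these statistics, along with measures of centre and spread. Its categorical analysis, based on ICH E14, covers QT and QTc only. It does not refer to Section 10. The only ECG concern display named in SAP Section 9 is "Listing of QTc data that meet criteria of potential concern as described in ICH E14".

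In the protocol, Section 2.2 makes ECG part of the primary endpoint. Section 9.3 plans mean changes in ECG measures and proportions meeting ICH E14 criteria. Section 7.1.2 has each tracing classed locally, and its on-study prompt to call the medical monitor uses QT and QTcF.

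**The concern.** PR and QRS are different intervals, yet they share one criterion word for word. Because the limbs are joined, a long absolute limit can make the relative limb redundant. For QRS this happens at every baseline below 160 msec, where the rule reduces to a QRS of at least 200 msec.

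The Section 10 row is the only rule in the plan that would sort subjects by QRS widening. If it is tabulated as written, it can show zero subjects of concern while several have widened well beyond the SAP's own 25% mark. For a primary safety endpoint, a reader could take that zero as reassurance that the rule is too insensitive to give.

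**Working it through.** **Inputs**

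- Absolute limb: 200 msec (SAP Section 10, QRS row).
- Relative limb: 25% increase from baseline (same row).
- Joined by *and* (same row).
- Baseline QRS, b: not given in the documents. The range 80 to 120 msec is an assumption for subjects without bundle branch block. Wider baselines are shown as well because protocol 4.2 states "Participants with known history of bundle branch block (either right or left) are allowed if absolute QTcF value does not exceed 500 msec", and also admits subjects with a functioning pacemaker.

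The plan states no figure of its own to reproduce.

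**Formulas**

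- Smallest flagged QRS = max(200, 1.25 × b).
- Rise needed = max(200, 1.25 × b)/b − 1.
- The relative limb first matters when 1.25 × b = 200, so b = 200/1.25 = 160 msec.

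**Results**

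| Baseline QRS (msec) | 25% limb alone reached at (msec) | Smallest flagged QRS (msec) | Rise needed for a flag |
|---|---|---|---|
| 80 | 100 | 200 | 150% |
| 100 | 125 | 200 | 100% |
| 120 | 150 | 200 | 67% |
| 140 | 175 | 200 | 43% |
| 160 | 200 | 200 | 25% |
| 180 | 225 | 225 | 25% |

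Below 160 msec, any QRS that reaches 200 msec has already risen by more than 25%, so the relative limb excludes nobody and adds nobody. This result needs no assumption about the baseline distribution.

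**Worked case.** Baseline 100 msec, on-treatment 150 msec: the rise is 150/100 − 1 = 50%. The relative limb is met (150 ≥ 125). The absolute limb is not (150 < 200). The subject is not flagged.

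**Is there another categorical QRS rule?** The ICH E14 categories in SAP 5.3.5, the concern listing in SAP Section 9 and the on-study prompt in protocol 7.1.2 all use QT or QTc. None uses QRS.

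**The case against.** The strongest reply is that QRS widening has other ways to surface. SAP 5.3.5 gives by-visit summaries of value and change, including the maximum. In the worked case the +50 msec would be the displayed maximum change if it were the largest at that visit, and a shift across all subjects would move the mean and median. Protocol 7.1.2 says "If the abnormal ECG measurements are considered as clinical significant, the abnormality will be recorded as AE in the eCRF", so such findings reach the adverse event tables. SAP 4.2 has medically qualified staff review ECG listings for signals. All of this stands. A reader might infer that conduction slowing cannot appear in the results at all; the documents do not support that. These routes do not supply a count, however. A mean dilutes change in a few subjects. A maximum is one value and may come from a subject with bundle branch block or pacing. The adverse event route depends on a local judgement of clinical significance.

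Second, SAP 5.3.5 never invokes Section 10 and no named display uses the QRS row, so a misleading zero may never be printed. That also stands. It limits the present harm and is part of what needs fixing.

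Third, pairing an absolute limit with a 25% change is the format for heart rate, PR and QRS alike, so it may be a deliberate choice for specificity. The documents cannot show whether the 200 msec limit was copied from PR by mistake. They do show that the pairing gives the relative limb no work to do for QRS below 160 msec.

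A reader might also take protocol 7.1.2 to require investigation of bundle branch block that appears on treatment: "If there is no known history of BBB (either right or left), the discovery of such should prompt further investigation". That sentence belongs to the paragraph on eligibility at the Baseline visit and concerns steps before screening proceeds. It does not set a rule for new block during treatment, nor does it show that the Section 10 row was meant to detect one.

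**Conclusion.** The point holds as a weakness of the categorical QRS criterion. The duplicated text, the redundancy of the 25% limb below a 160 msec baseline and the lack of any other categorical QRS rule follow directly from the documents. The required rise of 150% down to 67% holds only for an assumed baseline of 80 to 120 msec; it falls to 25% at 160 msec or more, which is possible among the subjects admitted with bundle branch block or pacing. If the row is reported, a zero count says little about conduction. Whether it would be reported is not settled by the SAP, and a clerical error is not proved. This is a cheap correction that should be made, and it leaves the rest of the ECG analysis as it is.

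**What to change.** 1. In SAP Section 10, list the two QRS limbs separately, as the QTc row already does for its absolute and change limits.
2. Count subjects with a QRS increase from baseline of at least 25% at any post-baseline ECG, by prior-treatment group and overall, with bundle branch block and paced subjects shown separately. The 25% figure is the SAP's own.
3. Have the sponsor confirm whether the 200 msec absolute limit was intended for QRS or carried over from PR. No replacement limit is proposed here.
4. Refer to the Section 10 ECG criteria from SAP 5.3.5, so that the count has a named place in the output.

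The cost is a few lines of SAP text and one extra count from intervals already recorded at Baseline, Months 6, 12, 18 and 24, and early termination. The downside is some flags from measurement noise at short baselines: at 80 msec, a 20 msec rise (0.25 × 80) is enough. The table should say so.

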6.1.2 Month 3 (\pm 14 days)

- ADAS-cog.
- C-SSRS.
- Review and record new concomitant medications.
- Assess symptoms/adverse events by asking the participants to respond to a non-leading question such as “How have you been feeling?”
- Brief physical and neurologic examination.
- Vital signs: blood pressure and pulse rate.
- Drug accountability. Any discrepancies are recorded in the source and the subject and caregiver/informant are counseled regarding proper dosing compliance.
- Dispense study drug. Subjects take their dose of study medication in the clinic.

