4.2.3 Vital Signs

Vital signs measurements consist of blood pressure and pulse rate. . In TTP488-303, the vital signs will be conducted at Months 3, 6, 9, 12, 15, 18, 21 and 24 or in the event of early termination. Variables of analysis will include means, mean changes over time, and proportions of subjects meeting criteria for potential clinical concern in vital signs:

- Mean and mean changes in systolic and diastolic blood pressures
- Mean and mean changes in pulse
- Proportions of subjects with treatment-emergent values or changes of potential clinical concern.

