5.3.2 Vital Signs

Subjects with vital signs meeting the criteria in Section 10 of this SAP for values of potential clinical concern will be flagged and summarized. Proportions of subjects with vital signs of potential clinical concern will be examined for the treatment groups.

No formal inferential statistics will be applied to the vital signs data.

For each post-Baseline assessment, descriptive statistics are provided for the assessment value and the change from Baseline to the assessment with mean, median, standard deviation, minimum, and maximum at each assessment time.

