Review Inclusion/Exclusion Criteria	X*									
Body weight	X		X		X		X		X	X
Brief Neuro & Physical Exams	X	X	X	X	X	X	X	X	X	X
Review Concomitant Medications	X	X	X	X	X	X	X	X	X	X
Blood Pressure and Pulse Rate (sitting or supine)	X	X	X	X	X	X	X	X	X	X
12 Lead ECG	X		X		X		X		X	X
Adverse Events Assessment	X	X	X	X	X	X	X	X	X	X
Study Drug Dispensing / Accountability	X*	X	X	X	X	X	X	X	X	X
Study Drug Dosing	X*	→	→	→	→	→	→	→		
MMSE	X		X		X		X		X	X
ADAS-cog	X	X	X	X	X		X		X	X
CDR	X		X		X		X		X	X
NPI	X		X		X		X		X	X
ADCS-ADL	X		X		X		X		X	X
COWAT	X		X		X		X		X	X
CFT	X		X		X		X		X	X
TMT	X		X		X		X		X	X
Columbia Suicide Severity Scale (C-SSRS)	X	X	X	X	X	X	X	X	X	X
RUD-lite	X		X		X		X		X	X
DEMQOL-proxy	X		X		X		X		X	X
Hematology	X		X		X		X		X	X
Blood Chemistry (incl HbA1c)	X		X		X		X		X	X
Pharmacokinetic Blood Sampling	X		X		X		X		X	X
Pharmacodynamic blood sampling (Aβ)	X		X		X		X		X	X

*procedures unique to OLE. All other baseline procedures are required TTP488-301 Month 18 procedures and are not repeated as part of the TTP488-303 baseline visit.

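### SAP Section 10 relies on ECG heart rate in place of a pulse criterion, but no ECG is scheduled at Months 3, 9, 15 and 21, so no rate criterion applies at 4 of the 8 scheduled post-baseline visits

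*SAP*

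**What the plan says.** SAP 4.2.3 names blood pressure and pulse as the vital signs and states that "the vital signs will be conducted at Months 3, 6, 9, 12, 15, 18, 21 and 24 or in the event of early termination". It plans "Mean and mean changes in pulse" and also "Proportions of subjects with treatment-emergent values or changes of potential clinical concern". The second variable carries no exclusion for pulse.

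SAP 5.3.2 says where the criteria come from: "Subjects with vital signs meeting the criteria in Section 10 of this SAP for values of potential clinical concern will be flagged and summarized". In Section 10 the vital-sign block has entries for systolic and diastolic pressure only. The note under the table places pulse among the parameters without a threshold: "pulse rate from VS (rely on ECG heart rate".

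The rate criterion that does exist sits in the ECG block of Section 10. Its lower limb is "<50 bpm and ≥/=25% decrease from baseline". Its upper limb is a rate above 100 bpm with a rise of at least 25% from baseline.

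The schedules in SAP Section 12 and Protocol Table 1 agree. The row "Blood Pressure and Pulse Rate (sitting or supine") is marked at baseline, every treatment visit and Early Termination. The ECG row is marked at baseline, Months 6, 12, 18, 24 and Early Termination. The visit list in Protocol 6.1.2 (Month 3) includes "Vital signs: blood pressure and pulse rate" and no ECG.

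**The concern.** The SAP does not treat heart rate as unimportant. It sets a rate criterion, and it exempts pulse on the ground that the ECG supplies the rate. That ground fails at every scheduled visit that has a pulse reading and no ECG.

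Protocol 2.2 lists vital signs and ECG among the primary endpoints, so the tables of potential clinical concern are part of the main safety output. Subjects who received placebo in TTP488-301 have their first scheduled on-drug assessment at Month 3, and that visit has no rate criterion. At stake is a by-group count of subjects with a marked rate change. A change seen only at a visit without an ECG does not enter that count.

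**Working it through.** The plan gives no figure to reproduce. The check compares the schedules and then asks what the missing criterion would have counted.

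**Step 1: coverage.**
- Pulse visits (SAP 4.2.3, SAP 12, Protocol Table 1): {3, 6, 9, 12, 15, 18, 21, 24}, 8 visits.
- ECG visits (SAP 12, Protocol Table 1): {6, 12, 18, 24}, 4 visits. The visit lists in Protocol 6.1.2, 6.1.4, 6.1.6 and 6.1.8 confirm that no ECG is scheduled at Months 3, 9, 15 and 21.
- Pulse visits without an ECG: {3, 9, 15, 21}, 4/8 = 50%.
- At Early Termination both are done (Protocol 6.2). Counting it as a visit type, a rate criterion is available at (4 + 1)/(8 + 1) = 5 of 9.

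**Step 2: timing for placebo crossovers.**
- First on-drug pulse: Day 90 ± 14, that is Days 76 to 104.
- First scheduled on-drug ECG: Day 180 ± 14, that is Days 166 to 194.
- Protocol 1.1.3 gives a mean half-life of 18 days in elderly participants. Day 90 is 90/18 = 5 half-lives. Assuming simple accumulation under once-daily dosing, exposure is then 1 − 0.5⁵ = 0.969, about 97% of steady state. Month 3 is therefore a reading at close to full exposure.

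**Step 3: what the criterion adds to the minimum and maximum.** It joins an absolute limit to a within-subject change. Take illustrative readings of 42 and 125 bpm.
- A reading of 42 qualifies only if (B − 42)/B ≥ 0.25, so B ≥ 42/0.75 = 56, where B is the subject's baseline. With B = 56 the fall is 14/56 = 25% and the subject counts. With B = 54 it is 12/54 = 22% and the subject does not.
- A reading of 125 qualifies only if (125 − B)/B ≥ 0.25, so B ≤ 125/1.25 = 100.

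A table showing a minimum pulse of 42 thus does not say whether that subject met the criterion, or how many subjects did. The minimum value and the minimum change may also come from different subjects.

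**Step 4: who is left out.** The subjects missed are those who meet the criterion at one or more of Months 3, 9, 15 and 21 and at no ECG. The documents give no rate of transient abnormalities, so their number cannot be computed.

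**Step 5: after the change.** Scheduled post-baseline visits with a rate criterion rise from 4/8 to 8/8.

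**The case against.** A reader might infer that pulse at these four visits goes unexamined. The documents do not support that:
- SAP 5.3.2 gives descriptive statistics, including minimum and maximum, for value and change at each assessment.
- SAP Section 9 plans a vital-signs listing that is not restricted to flagged values.
- SAP 4.2 has medically qualified reviewers read the listings for signals and has untoward findings reported as adverse events, so a rate abnormality judged to be one enters the adverse-event proportions.
- Protocol 9.6 gives the data monitoring committee the safety data.

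An extreme reading at Month 3 would be visible, and this part of the objection stands. These safeguards still do not yield the number of subjects per group who met a fixed criterion.

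The exemption is also an openly stated choice. Protocol 9.3 commits only to mean changes in vital signs. The ECG rate is taken supine after rest (Protocol 7.1.2), whereas pulse may be taken sitting or supine (Protocol 7.1.1). Preferring the more standardised measure is defensible, and the plan does not contradict itself. But that reasoning works only where an ECG exists.

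A persistent change would probably appear at the next ECG, and Protocol 6.2 calls for an ECG at Early Termination. Only transient abnormalities, and subjects lost before Month 6 without a final visit, escape the flag. This limits the gap but does not close it, since Protocol 6.3 has the final visit requested of a withdrawing participant.

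Finally, the documents report no heart-rate signal. The earlier safety findings in Protocol 1.1.3 are falls, confusion and ADAS-cog worsening at 20 mg/day.

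**Conclusion.** The point holds as a limited coverage gap. No threshold criterion applies to pulse at any visit, and the stated substitute is unavailable at 4 of 8 scheduled post-baseline visits. A subject with an abnormal rate only at those visits is left out of every proportion of potential clinical concern.

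It is tempting to go further and say that the planned proportion of subjects with abnormal heart rate is understated. A count restricted to ECG visits can miss subjects that an all-visit count would include. However, the only rate criterion in the plan is an ECG criterion, and it can be applied at every scheduled ECG. The documents give no basis for the size of any shortfall, and 50% is a share of visits, not of subjects. No biased result has been demonstrated.

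The conclusion assumes that no unscheduled ECGs are taken at the four visits. It also takes the Section 10 heart-rate entry as the definition of the ECG flag, because SAP 5.3.5 does not restate it. The gap is worth closing because doing so is cheap and the display serves a primary endpoint.

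**What to change.** In SAP Section 10, remove the pulse exemption. Apply the existing heart-rate criterion (below 50 bpm with at least a 25% decrease, or above 100 bpm with at least a 25% increase) to vital-sign pulse at every visit. Use baseline vital-sign pulse as the reference, not baseline ECG rate, because the two may be taken in different positions. Protocol 7.1.1 asks for the same position at all visits.

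Report the result under SAP 5.3.2 as a row separate from the ECG-based flag. Do not add the two rows, because they overlap at Months 6, 12, 18, 24 and Early Termination.

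The cost is one line in Section 10 and one row in the vital-signs table, with no new data or visits. The downside is that a few more subjects will be flagged, on a reading less standardised than the supine ECG. If the exemption is kept, SAP 4.2.3 and 5.3.2 should at least state that the proportions exclude pulse and that Months 3, 9, 15 and 21 carry no rate criterion.
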